- 4. Develop, implement and assess strategies to recruit, train, and integrate peer CHW health coaches within the PCMH model.

The 36-month intervention will be conducted using a staggered entry design across four, overlapping, 12-month waves to account for CHW caseload limits. This study will test a scalable model of peer health coaching to address the millions of patients at risk for DM, using low cost, culturally congruent personnel to promote prevention of DM in PCMH practice. If successful, our study team will work with VA's Central Office and NY City's Health and Hospital Corporation to translate the model for larger scale implementation.

Characteristics of the Research Population

Number of Subjects

All 12 PC teams at VA NY Harbor and all 4 PCMH teams at BH will be eligible to participate. In our VA PROVE study, 51/52 PCPs participated in the intervention, and we expect similar rates in this project. Eligible patients will be identified through the study's pre-DM registry, which will be based on the EMR and Corporate Data Warehouse (CDW) at each site. This methodology builds on our ongoing national, retrospective cohort study of predictors of DM among veterans with pre-DM back to 2008. Based on preliminary analysis of VA NYHHS data from 2010-2012, 62% of veterans enrolled in PC without DM, have had an HbA1c test in the previous two years.

In the intervention group, we anticipate contacting 2,100 randomly selected patients (1,050 at the VA* and 1,050 at BH) to ultimately enroll about 1,100 patients (550 at the VA and 550 at BH). This outreach sample reflects our assumption that 20% of patients will be unreachable and that 60% of those reached will enroll in the study. Another 1,100 patients attributed to control group providers will be randomly selected as the control group, in accordance with the waiver of HIPAA authorization. As detailed below, the control group will not participate in the CHW intervention. The total sample, including the intervention and control groups, will be about 2,200 patients. This amounts to approximately 265 patients (across intervention and control groups) per wave and per clinical site.

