Influence of neighborhood factors: To examine the influence of contextual factors on implementation and intervention effectiveness, we will conduct population-level analysis of variation in implementation and health outcomes across NYC neighborhoods. We will conduct this analysis with patient data available at the start of the study and data on enrolled patients post-intervention. To obtain information on neighborhood-level factors, we will use publically available data on social and environmental aspects of NYC neighborhoods in the FACETS database (data accessible at <https://github.com/mcantor2/FACETS>). We will map patient addresses to census tracts, aggregate census tracts to neighborhoods, and statistically examine the association of neighborhood-level contextual factors on prediabetes prevalence across NYC. Patients' location information will be used at an aggregate neighborhood level, and it will not be possible to identify their precise location in the city. Individual patients and their PHI will not be identifiable.

Data Analysis and Data Monitoring

The analytic methods described below are designed to test the primary hypotheses that prediabetic patients cared for by PCMH teams randomly allocated to the CHW Coaching group, will have lower annual hazard rate of incident cases of DM overtime more weight loss, and higher PAM scores by the end of the intervention

period than similar patients cared for by PCMH teams allocated to the Control group, adjusting for baseline rates. The unit of analysis is patients, aggregated to the provider level.

Analysis: Patient Clinical Outcomes and Health Behaviors

Descriptive analysis techniques (measures of central tendency and variability, frequencies and proportions) will be used to present baseline characteristics of participants (patients and their PC staff) in the control and intervention arms. Chi-square tests and t-tests will be used to check if these baseline characteristics are balanced between the two study groups. For continuous outcomes, normal assumptions will be checked, and non-parametric alternatives and transformations will be considered as needed.

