To assess the overall effectiveness of the CHW intervention we will compare cumulative DM incidence rates and time to DM incidence (in addition to other outcomes: weight loss, obesity rate, and health care utilization) between the two study groups, using intention-to-treat and per protocol analyses. Time to DM incidence at 12-month follow-up of the intervention and control arms, aggregated across the 4 study waves, will be compared using Cox proportional hazard regression models. Chi-square analyses will be conducted to compare outcomes between the two groups for categorical variables (e.g. obesity rate, PAM stage) and t-tests will be conducted for continuous outcomes (e.g. weight change, PAM score). We will then conduct (generalized) linear mixed-effects modeling, which will (1) take into account the intra-cluster correlation coefficient (ICC) of patients within providers and teams, (2) analyze repeated measures at several time-points (baseline, midpoint, and post-intervention) simultaneously, (3) include team or patient level baseline covariates easily, if they are found to be unbalanced between two arms, and (4) deal with attrition problems and other missing data automatically. For categorical outcomes, such analyses will be implemented using SAS Proc GLIMMIX, while using SAS Proc MIXED for continuous outcomes.

We will use multilevel survival analysis to determine the effect of the intervention on time to DM, as patients are enrolled in waves and the time to DM incidence may be censored by the end of study. Specifically, we will fit Cox proportional hazard regression models with mixed effects to examine the hazard ratio between two groups, adjusting for important covariates and taking into account the correlation among patients within teams.

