While the above inclusion and exclusion criteria return about 9,300 eligible patients, 8,200 at BH and 1,100 at the VA, CHW caseload limitations preclude us from reaching all these eligible patients during the 3-year intervention. Assuming a caseload of 72 patients per fulltime CHW per wave (with 3.5 fulltime equivalent CHWs across both sites and 4 waves), the intervention is projected to enroll a minimum of 1,008 subjects into the intervention group. An equivalent number of subjects will be randomly selected from the Control teams for a total of at least 2,016 study subjects overall. The intervention and control subjects will be split across the two study sites. After assuming that we will not be able to reach about 20% (due to missing or incorrect contact information) unreachable rate, and that about 60% will consent to enroll in the intervention, we will randomly select about double the 1,008 subjects (about 2,100) for potential enrollment into the intervention in order to enroll the minimum of 1,008 intervention subjects needed to have adequate statistical power.

Power: In the pre-DM population we estimate the 3-year DM incidence to be 15% (based on preliminary analysis of a similar VA cohort from 2010-2012). Based on our analyses, with 1,008 patients allocated to each of the intervention and control groups, we anticipate having 80% power ($\alpha = 0.05$) to detect a difference in time-to-event (DM incidence) between the intervention and control group.

To assess measures of implementation fidelity, specifically coverage, duration, and frequency of CHW-patient contact, we will base calculations on all patients enrolled. Since we will use all available study data from the electronic medical records, power and sample size considerations do not apply. We will assess content of CHW-patient contact using qualitative methods, hence power and sample size considerations do not apply.

To examine the variation in prediabetes prevalence across NYC neighborhoods, we will use available data from BH at the start of the study, in approximately 19,000 patients. These patients meet the study's previously stated eligibility criteria, with two modifications: patients must have (1) any HbA1c result in the past 5 years and (2) an address available in the EHR. Data on all enrolled BH patients at the end of the study, an estimated 1,000 patients, will also be used. Since we will use all available study data, power and sample size considerations do not apply.

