All primary care staff will be given information about the proposed research during regular staff meetings, email announcements and a study flyer and then asked to participate. Staff providing verbal consent to participate will be randomized (as part of their PACT team) to either work with a CHW or serve as controls. Staff who opt-out will not be randomized, although might still work on a team that is included in the study. For example, if one primary care provider in a team declines participation, the other providers and team members consent, the team will be randomized to a study arm. If that team is randomized to an intervention arm, the

CHW would only work with the patients of the consenting providers. We anticipate that we will be able to obtain sufficient numbers of staff consenting to participate, as in our previous panel management study only one PCP out of fifty-one declined, and a majority of staff reported that the interventions and CHW support were helpful. Lastly, as CHWs will be extending services and interventions that are a part of regular, evidence-based practice on behalf of patients' primary care physician, patients will not individually consent to receiving phone calls, mailings, or any other contact with the CHW. For surveys, which are research procedures specific to this study, consenting elements will be presented at the top of the survey. Primary care teams will pre-approve all lists of patients receiving interventions as well as approving the content of the CHW's intervention. Patients will have the right to opt out of receiving outreach at any time. All mail materials will include instructions on how to stop receiving mail from the CHW.

A waiver of authorization for both recruitment/identification purposes and for study procedures has been sought. We use the electronic medical record to generate a list of eligible participants, in order to approach them to screen for eligibility. Without the requested Waiver, screening could not be practically carried out and would adversely affect the scientific rigor of the study.

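### With at most 16 randomised teams, no small-sample method is set for the mixed Cox, MIXED and GLIMMIX tests of arm, so control of the 5% level is not assured

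*Combined protocol and SAP*

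**What the plan says.** **What is randomised.** Under Method of Subject Identification and Recruitment, and Consent, consenting staff are "randomized (as part of their PACT team) to either work with a CHW or serve as controls". Number of Subjects gives the supply of clusters: "All 12 PC teams at VA NY Harbor and all 4 PCMH teams at BH will be eligible to participate". That is 16 teams at most.

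**Where the patients sit.** The same section expects the intervention arm to "enroll about 1,100 patients (550 at the VA and 550 at BH", with a control group of the same size. Statistical Power and Sample Size makes its power statement "with 1,008 patients allocated to each of the intervention and control groups" and puts the pool at "about 9,300 eligible patients, 8,200 at BH and 1,100 at the VA".

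**How arm is tested.** Under Analysis: Patient Clinical Outcomes and Health Behaviors, the clustered analysis of time to diabetes is "we will fit Cox proportional hazard regression models with mixed effects to examine the hazard ratio between two groups", with patients in the same team treated as correlated. The other outcomes get mixed models that allow for correlation within providers and teams. For categorical outcomes "such analyses will be implemented using SAS Proc GLIMMIX, while using SAS Proc MIXED for continuous outcomes".

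**Unit of analysis.** The opening of Data Analysis and Data Monitoring says: "The unit of analysis is patients, aggregated to the provider level".

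The documents give no ICC value, degrees-of-freedom method, small-sample correction, permutation test or rule for balancing teams within site.

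**The concern.** Arm is constant within a team, so the arm effect is a between-team contrast. Its precision is estimated from at most 16 team results, however many patients each team supplies. A test that refers the estimate to a normal distribution, or to a t distribution with about 2,000 patient-level degrees of freedom, treats the between-team variance as nearly known. Each team-level covariate added for imbalance, which the plan allows, uses one more of the few degrees of freedom.

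The mixed models are the analyses a reader will trust, because they are the ones meant to respect the cluster design. If their reference distribution is wrong, an effect on diabetes or weight may be declared too often, with intervals too narrow. The provider-level sentence adds a second uncertainty, over which unit carries the inference.

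**Working it through.** **1. The plan's own figures.** The sample size reproduces: 72 patients × 3.5 CHWs × 4 waves = 1,008 per arm, 2,016 in all. The 80% power cannot be reproduced, because no hazard ratio is stated.

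**2. Inputs.**
- Teams: 12 + 4 = 16. An even split, 6:6 at the VA and 2:2 at BH, is assumed; the documents do not state one.
- Patients: half per site. The documents state this for the intervention arm. The figure of about 265 patients per wave and site, both groups together, points the same way (265 × 4 = 1,060 at each site). BH teams then average 1,008/4 = 252 patients and VA teams 1,008/12 = 84. Any shortfall from the VA pool of 1,100 would put more weight on the four BH teams.
- Event rate: 15% at 3 years. With a constant hazard, −ln(0.85)/3 = 0.0542 per year. The 12-month risk is 1 − exp(−0.0542) = 5.27%, or about 106 events in 2,016 patients.
- Between-team variation: not given, so a range is assumed.

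**3. Rough size.** Team-level degrees of freedom are 16 − 2 = 14, or 16 − 3 = 13 with a site term. P(|t14| > 1.96) = 7.0% and P(|t13| > 1.96) = 7.2%. The correct critical values are 2.14 and 2.16.

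**4. Time to diabetes, 12 months, null simulation.** Two stand-ins for the mixed Cox model were used: an exponential model with gamma team frailty (1,000 to 2,000 runs per setting, without and with a site term) and a Poisson model with normal team effects. The ICC is approximated as risk × SD², for example 0.0527 × 0.25² = 0.0033.

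| SD of log team hazard | Approx. ICC | Gamma, Wald z | Poisson-normal, Wald z | Gamma, t on 14 or 13 df |
|---|---|---|---|---|
| 0 | 0 | 4.0–4.3% | about 5% | 2.3–2.6% |
| 0.15 | 0.001 | 5.6–6.1% | 5.7% | 3.2–3.9% |
| 0.25 | 0.003 | 6.8–7.9% | 8.5% | 4.7–6.0% |
| 0.40 | 0.008 | 9.1–9.9% | 11% | 6.3–6.6% |

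The t reference removes most of the excess, but not all of it when teams differ strongly.

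**5. Continuous outcome, linear mixed model with random team, null simulation (4,000 runs).** With about 2,000 patient-level degrees of freedom, t is in effect z.

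| ICC | z | t on 14 or 13 df |
|---|---|---|
| 0 | 3.9–4.1% | 2.4–2.5% |
| 0.001 | 4.6% | 2.8–3.2% |
| 0.005 | 6.7–6.9% | 4.4–4.7% |
| 0.01 | 7.3–7.7% | 5.2–5.3% |
| 0.02 | 7.3–7.5% | 5.1–5.2% |
| 0.05 | 6.7–7.2% | 4.7–4.9% |

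Monte Carlo error in both tables is about 0.3 to 1 percentage point. GLIMMIX for a categorical outcome was not simulated.

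**6. The unit, side by side.** Randomisation is by team. The opening of the analysis section aggregates to provider. The mixed models for other outcomes use providers and teams; the mixed Cox model uses teams. Under Attrition/missing data, a provider who changes arm keeps earlier patients in the old arm while later ones enter the new arm. Such a provider has patients in both arms, so aggregation to provider is not well defined.

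**7. Is a permutation test feasible?** Balanced within site: C(12,6) × C(4,2) = 924 × 6 = 5,544 allocations. Unrestricted, 8 of 16: C(16,8) = 12,870. Either is ample. A within-site permutation test gave 4.1–5.0% in null simulation (600 to 800 runs).

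**The case against.** The strongest reply is that silence is not error. The plan names mixed models with team effects, which is the right family, and a programmer may well choose suitable degrees of freedom. Every inflated rate above also rests on a variance that the documents do not supply. Both points stand, and they limit what can be claimed.

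Four stronger readings are tempting, and the documents do not support them.

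- **That the 5% level is breached.** This depends on the unknown between-team variance. With none, the tests run at about 4–5%; the linear model stays below 5% at ICC 0.001.
- **That MIXED and GLIMMIX will use large-sample tests.** The plan names only the procedures. Their denominator for arm depends on the degrees-of-freedom method and on how the team effect is coded. The gap is an unspecified method, not a demonstrated error.
- **That the provider-level sentence settles the analysis.** If provider were the only random effect, with 3 or 4 providers per team and ICC 0.01–0.02 assumed, the error rate would be 4.6–5.9% with all clustering between providers and 15–20% with all of it between teams. But the detailed text puts teams in its models, so the sentence is an inconsistency to reconcile. No t-test on provider means is planned.
- **That longer follow-up makes matters worse.** A mean of 24 months would raise the rates, but the diabetes comparison is stated at 12 months.

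The plan's first-step Cox, chi-square and t-tests, which ignore clustering, carry a larger risk. They are a separate matter, and repairing them would leave this gap open.

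**Conclusion.** The point holds as one of assurance. With at most 16 teams, the planned test of the main outcome is of a type whose usual reference is large-sample, and nothing in the plan corrects for that. At 12 months the false-positive rate is about 4–5% with no team variation, 6% at an SD of log hazard of 0.15, 7–9% at 0.25 and 9–11% at 0.40. An SD of 0.25 corresponds to an ICC of only about 0.003, so modest team differences are enough. For linear models the choice of reference decides the matter: about 7–8% with z or patient-level degrees of freedom at ICC 0.005–0.05, and at or near 5% on 13–14 team-level degrees of freedom.

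These figures assume 16 participating teams split evenly within site, half the patients at each site, two-sided tests, a constant hazard, and stand-in models for the mixed Cox fit. The provider-level sentence conflicts with the randomisation and with the plan's own models. The change is advisable and should be made before the analysis.

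**What to change.** 1. Replace the provider-level sentence with: analysis at patient level, with the randomised team as cluster and unit of inference. Attribute each patient to the team at enrolment, so that providers who change arm cause no ambiguity.
2. For MIXED and GLIMMIX, require Kenward-Roger or between-team degrees of freedom for arm.
3. For diabetes, take the p-value from a team-level permutation test over the allocations that the actual randomisation allowed: 5,544 if it was 6:6 and 2:2 within site, 12,870 if 8 of 16 were drawn without restriction. State which applies.
4. Report the mixed Cox hazard ratio with a team-level t reference, or with an interval obtained by inverting the permutation test.

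The cost is SAP wording, some programming (more if the permutation test is inverted for an interval) and slightly wider intervals. No new patients or data are needed.

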We will use a similar generalized linear mixed-effects modeling for the secondary outcomes, to explore the relationship of the intervention's effectiveness to specific patient and provider or team characteristics. We will investigate interactions between the intervention and the patients' level of activation, co-morbidities (HTN, depression, and smoking), and health care utilization. We will also test the correlation (Pearson's r) of provider self-efficacy and team collective-efficacy on patient outcomes. We will conduct secondary analyses to better understand the impacts of the individual components of this complex set of interventions. While designed to test the effectiveness of an overall strategy, we will seek to determine which of the intervention elements and dose of intervention (e.g. number of phone contacts, number of mailings, successful referral to *MOVE!*, Healthy Lifestyles, DPP or other programs) were most strongly associated with any improved outcomes. We will also conduct subgroup analyses to see which subgroups may benefit more from the intervention than the others. Such group analyses are data dredging; they should be considered as exploratory analyses and any resulting findings should be confirmed by independent studies.

Because control patients are not surveyed, follow-up survey data for a given wave will serve as the control group for the following wave's baseline survey data. For example, wave 1 follow-up data will be compared against wave 2 baseline data. The data collected in the survey are secondary outcomes.

Attrition/missing data: Although the retention of patients with specific provider panels is relatively stable at the VA and BH, there are a number of reasons for changes including moving, entering a nursing home or rehab facility, not being seen in PC for >2 years, or requiring specialty-based PC. Patients seldom switch among teams or providers within teams, limiting the potential for contamination between study groups. In our VA study of panel management (PROVE), only 7% of 9,841 hypertensive patients switched teams over 12 months of follow-up. In the event that a provider changes teams and moves from one study arm to the other, patients of theirs already enrolled in the study will remain in the study arm in which they were enrolled. In waves after a

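### Pearson's r for staff efficacy against patient outcomes makes no allowance for clustering, so a score shared within a team is tested too liberally whether patient rows or provider means are used

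*Combined protocol and SAP*

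**What the plan says.** The section Analysis: Patient Clinical Outcomes and Health Behaviors describes generalized linear mixed models for secondary outcomes and then adds: "We will also test the correlation (Pearson's r) of provider self-efficacy and team collective-efficacy on patient outcomes". The sentence gives no unit of analysis, cluster adjustment, covariates or named outcomes.

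Three other places bear on it:

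- Earlier in the same section, the mixed models are chosen partly because they "take into account the intra-cluster correlation coefficient (ICC) of patients within providers and teams". The Cox model for time to diabetes also has mixed effects, for correlation within teams.
- Data Analysis and Data Monitoring says of the analysis as a whole: "The unit of analysis is patients, aggregated to the provider level".
- Analysis: Intervention Implementation shows that both efficacy scores come from staff surveys. They describe providers and teams, not patients.

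On size, Number of Subjects says "All 12 PC teams at VA NY Harbor and all 4 PCMH teams at BH will be eligible to participate", and Statistical Power and Sample Size gives enrolment "for a total of at least 2,016 study subjects overall".

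**The concern.** The usual test of Pearson's r assumes independent pairs. Here the predictor belongs to a provider or a team and is repeated for every patient under that provider or team, while outcomes of patients in the same team are correlated. A predictor that is constant within clusters is the case in which ignoring clustering does most harm: chance differences between a few teams can look like an association with staff efficacy.

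The plan also hypothesises that the intervention raises staff efficacy. A correlation pooled over arms and sites could therefore partly reflect arm or site, and a bare correlation coefficient cannot adjust for either.

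What is at stake is a secondary finding about implementation: a reported link between staff efficacy and patient outcomes whose p-value is too small.

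**Working it through.** **Inputs from the documents.** Teams: 12 + 4 = 16 at most. Patients: the caseload statement, "Assuming a caseload of 72 patients per fulltime CHW per wave (with 3.5 fulltime equivalent CHWs across both sites and 4 waves", gives 72 × 3.5 × 4 = 1,008 in the intervention group. Since "An equivalent number of subjects will be randomly selected from the Control teams", the total is 2 × 1,008 = 2,016, which reproduces the plan's figure. Number of Subjects anticipates about 2,200; the smaller figure is used here. Average patients per team: 2,016 / 16 = 126.

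**Assumptions.** The documents give no ICC, so 0.01, 0.02 and 0.05 are used as a range. They give no provider count for this trial, so 52 is borrowed from the earlier VA study mentioned under Number of Subjects: 2,016 / 52 = 38.8 patients per provider and 52 / 16 = 3.25 providers per team. Collective efficacy is taken as one value per team.

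**Team score on patient rows.** Design effect = 1 + (126 − 1) × ICC. True type I error of a nominal 5% test ≈ 2 × [1 − Φ(1.96 / √design effect)].

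- ICC 0.01: 1 + 1.25 = 2.25; error 19%.
- ICC 0.02: 1 + 2.50 = 3.50; error 29%.
- ICC 0.05: 1 + 6.25 = 7.25; error 47%.

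**Team score on provider means.** Two provider means in the same team have correlation c = ICC / [ICC + (1 − ICC)/38.8], and the design effect is 1 + (3.25 − 1) × c.

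- ICC 0.01: c = 0.01 / (0.01 + 0.0255) = 0.28; design effect 1.63; error 13%.
- ICC 0.02: c = 0.02 / (0.02 + 0.0253) = 0.44; design effect 1.99; error 17%.
- ICC 0.05: c = 0.05 / (0.05 + 0.0245) = 0.67; design effect 2.51; error 22%.

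**Simulation under no association** (16 teams, 52 providers, 2,016 patients, team-level ICC only, 4,000 runs each):

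| Score and unit | ICC 0.01 | ICC 0.02 | ICC 0.05 |
|---|---|---|---|
| Team score, patient rows | 20% | 30% | 48% |
| Team score, provider means | 14% | 17% | 24% |
| Team score, team means (n = 16) | 5% | 6% | 5% |
| Provider score, patient rows | 9% | 14% | 23% |
| Provider score, provider means | 4% | 6% | 5% |

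A separate simulation gave 19%, 28% and 47% for the first row and 12%, 17% and 23% for the second, hence the rounded ranges of 19–47% and 12–24%. Adding provider-level correlation raises the provider score's error on patient rows, for example to 14% with 0.01 at each level.

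**What the unit does to the threshold.** The two-sided 5% critical value is |r| = t / √(n − 2 + t²). It is 0.044 for n = 2,016, 0.273 for n = 52 and 0.497 for n = 16.

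**The case against.** A reader might infer that the plan treats about 2,000 patients as independent observations. The documents do not say so. The correlation sentence names no unit, and the general statement about aggregating to the provider level can be read as correlating provider mean outcomes. On that reading the test of provider self-efficacy is sound at about 5%. This part of the objection stands. It does not rescue the team score, because providers in one team share it and their mean outcomes are correlated.

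A reader might also apply the 16-team limit and the 19–47% range to both scores. That is too strong: self-efficacy varies by provider, so its sample is the number of responding providers, nested in teams.

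The documents do not state that collective efficacy is one value per team. The survey scores are analysed elsewhere with adjustment for staff role, which suggests individual responses. If individual values were kept, the inflation should lie between the team-score and provider-score rows, depending on how alike answers are within a team.

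The average of 126 per team is a simplification. With an equal split between sites, team sizes would be nearer 1,008 / 12 = 84 at the VA and 1,008 / 4 = 252 at Bellevue. The size-weighted mean is then (12 × 84² + 4 × 252²) / 2,016 = 168, and the patient-row design effect at ICC 0.01 is 1 + 167 × 0.01 = 2.67 rather than 2.25. The simplification does not exaggerate the problem.

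Finally, mixed models relating effectiveness to provider or team characteristics are planned just before this sentence, so the correlation is supplementary. That is fair and limits its importance. Those models address whether the intervention works better in some settings, however, not whether efficacy is associated with outcomes. The plan's caution about data dredging is attached to the subgroup analyses and does not expressly cover this test.

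**Conclusion.** The point holds for the team score under either reading of the unit: a nominal 5% test has a true error of about 19–47% on patient rows and about 12–24% on provider means, against about 5% on at most 16 team means. For provider self-efficacy it holds only if patient rows are used (about 9–23%). The figures rest on assumed ICCs of 0.01–0.05, an assumed 52 providers, equal-sized teams and a collective-efficacy score shared within the team.

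Two further inferences are not supported. The plan gives no decision rule or causal claim for this correlation, so it does not say that staff efficacy would be declared to drive outcomes. Nor does it say that Pearson's r will be applied to time to diabetes; it refers only to patient outcomes in general. If time to diabetes is among them, Pearson's r cannot handle the censoring that the plan expects.

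This is a minor but worthwhile correction to a supplementary analysis. The primary comparison and the sample size are not touched.

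**What to change.** Replace the Pearson test by entering provider self-efficacy and team collective efficacy as provider- and team-level covariates in the mixed models already planned. Include random effects for provider and team, adjust for arm and site, and use small-sample degrees of freedom. If time to diabetes is among the outcomes, use the planned mixed-effects Cox model for it. State how individual survey responses are combined into a team score, and which outcomes are examined.

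A simpler alternative for the team score is to correlate it with team mean outcomes and state that n is at most 16.

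The change needs no new data. Its cost is wider intervals and low power for the team score: with 16 teams, |r| must exceed 0.497 to reach significance, and a true correlation of about 0.65 is needed for 80% power. That reflects the information the design holds on this question, and the report should present the result accordingly.
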